**Table 11-4 Criteria for Potentially Clinically Significant Electrocardiograms**

Parameter	Unit	Higher Limit
QRS interval	msec	$\geq 150$
PR interval	msec	$\geq 250$
QTcB	msec	$> 500$
QTcF	msec	$> 500$

QTc = QT interval corrected for heart rate.

QTcB = QT interval corrected for heart rate using the Bazett formula.

QTcF = QT interval corrected for heart rate using the Fridericia formula.

A listing of all AEs for participants with PCS ECG values will also be provided.

A shift table from baseline to the end of double-blind treatment period in the investigator's overall interpretation of the ECG will be presented by treatment group for the following categories: normal; abnormal, not clinically significant; abnormal, clinically significant. A tabular display of participants with postbaseline clinically significant ECG abnormalities according to the investigator's overall interpretation will be provided.

## 11.5 Other Safety Parameters

### 11.5.1 Brief Psychiatric Rating Scale—Positive Symptoms Subscale

Descriptive statistics for BPRS+ score and changes from the baseline values at each assessment time point will be presented by treatment group. BPRS+ total score is defined as the sum of 4 positive individual scores including suspiciousness, unusual thought content, hallucinations, and conceptual disorganization. If more than 1 item is missing, then the total score will be set to missing.

### **11.5.2 Clinician Administered Dissociative States Scale**

Descriptive statistics for CADSS score and changes from the baseline values at each assessment time point will be presented by treatment group. CADSS total score is the sum of scores for 23 subjective items. If more than 4 items are missing, then the total score will be set to missing.

### **11.5.3 Symbol Digit Coding**

Descriptive statistics will be presented at each assessment timepoint by treatment for the SDC parameters including the number of symbols completed, the rate of completion (number of symbols completed/time of trial), the number of corrected responses (symbols completed correctly), and the number of errors (symbols completed incorrectly).

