#### 4. Objectives and Endpoints

The primary objective is to evaluate the efficacy, as measured by improvement in MADRS total score, at 1 day post initial oral dose of AGN-241751 compared with placebo in participants with MDD. The key secondary objective is to evaluate the efficacy at Week 3 of AGN-241751 administered orally once a week compared with placebo in participants with MDD.

Objectives	Endpoints
Primary	

 
To evaluate the efficacy at 1 day post initial oral dose of AGN-241751 compared with placebo in participants with MDD
 
	
 
Change from baseline in MADRS total score at 1 day after first dose
 

Key Secondary	

 
To evaluate the efficacy at Week 3 of AGN-241751 administered orally once a week compared with placebo in participants with MDD
 
	
 
Change from baseline in MADRS total score at Week 3
 

Additional	

 
Additional endpoints to be explored to determine differences between AGN-241751 vs. placebo
 
	
 
Change from baseline in MADRS total score at 4 hours post dose, and on Study Days 5, 8, 9, 12, and 15
 
Change from baseline in Clinical Global Impressions-Severity (CGI-S) at 4 hours post dose, and on Study Days 2, 5, 8, 9, 12, 15, and 22
 
Rate of sustained responders during treatment
 
Rate of responders at 4 hours post dose, and on Study Days 2, 5, 8, 9, 12, 15, and 22
 
Rate of sustained remitters during treatment
 
Rate of remitters at 4 hours post dose, and on Study Days 2, 5, 8, 9, 12, 15, and 22
 
Time to first response
 
Time to first sustained response
 
Time to first remission
 
Time to first sustained remission
 

Objectives	Endpoints
Safety Measures	

• Adverse event (AE) recording, clinical laboratory measures, vital sign parameters, electrocardiograms (ECGs), and physical examinations

• Measure of psychotomimetic effects: Brief Psychiatric Rating Scale Positive Symptoms subscale (BPRS+)

• Measure of dissociative effects: Clinician Administered Dissociative States Scale (CADSS)

• Measure of suicidality: Columbia-Suicide Severity Rating Scale (C-SSRS)

• Measure of cognition/psychomotor function: Symbol Digit Coding (SDC)

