#### 10.4.2.5. Other Safety Parameters

Other safety parameters include the BPRS+, CADSS, C-SSRS, and SDC.

Descriptive statistics of actual values and change from baseline for BPRS+ total score will be presented at each assessment timepoint by treatment.

Descriptive statistics of actual values and change from baseline for CADSS total score will be presented at each assessment timepoint by treatment. The CADSS total score is defined as the sum of scores for 23 subjective items.

The number and percentage of participants with suicidal ideation or suicidal behavior as recorded on the C-SSRS will be summarized by treatment. The distribution of responses for most severe suicidal ideation and most severe suicidal behavior during the participant's lifetime, during the double-blind treatment period, and during the safety follow-up period will also be presented by treatment. Supportive listings will be provided and will include the participant number, lifetime history, and postbaseline values. Intensity of suicidal ideation, suicidal behavior type, and lethality of suicidal behavior will also be included in these listings. A listing of all AEs occurring in participants who have suicidal ideation or suicidal behavior will also be provided.

Descriptive statistics will be presented at each assessment timepoint by treatment for the SDC parameters including the number of symbols completed, the rate of completion (number of

symbols completed/time of trial), the number of corrected responses (symbols completed correctly), and the number of errors (symbols completed incorrectly).

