## 11 Safety Analyses

The safety analysis will be performed using the Safety Population. The safety parameters will include adverse events (AEs), clinical laboratory, vital sign, electrocardiographic (ECG), BPRS+, CADSS, C-SSRS, and SDC parameters. For each safety parameter, except AEs, the last nonmissing safety assessment before the first dose of double-blind study treatment will be used as the baseline for all analyses of that safety parameter. Continuous variables will be summarized by number of participants and mean, SD, median, minimum, and maximum values. Categorical variables will be summarized by number and percentage of participants.

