## **14 Determination of Sample Size**

The sample size of approximately 50 randomized participants in each of the 5 treatment groups is not based on statistical power consideration due to the lack of information of AGN-241751 for the variability of change from baseline to 1 day after first dose in MADRS total score.

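### Symbol Digit Coding is summarised by timepoint only, without change from baseline, so the collected baseline is not used to sharpen the cognitive safety comparison

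*SAP*

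**What the plan says.** Protocol section 4 assigns cognition and psychomotor function to SDC among the safety measures. The schedules of activities in both documents place the test at Visit 1 (Screening) and Visit 9/ET only, so each participant has one planned pre-dose and one planned post-dose result.

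SAP 11.5.3 gives the whole analysis in one sentence: "Descriptive statistics will be presented at each assessment timepoint by treatment for the SDC parameters including the number of symbols completed", followed by the completion rate and the counts of correct and wrong responses. Protocol 10.4.2.5 agrees. Neither mentions change from baseline for SDC.

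The neighbouring scales are treated differently:

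- BPRS+ (SAP 11.5.1): "Descriptive statistics for BPRS+ score and changes from the baseline values at each assessment time point will be presented by treatment group".
- CADSS (SAP 11.5.2): "Descriptive statistics for CADSS score and changes from the baseline values at each assessment time point will be presented by treatment group".
- CADSS (protocol 10.4.2.5): "Descriptive statistics of actual values and change from baseline for CADSS total score will be presented at each assessment timepoint by treatment".

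Both documents also plan change from baseline for laboratory, vital-sign and ECG values.

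A baseline for SDC is already defined. For every safety parameter except AEs, SAP section 11 says that "the last nonmissing safety assessment before the first dose of double-blind study treatment will be used as the baseline for all analyses" of that parameter. For SDC that is ordinarily the Visit 1 test.

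**The concern.** SDC is a timed test in which the participant enters as many correct digits as possible in 120 seconds. People can be expected to differ in processing speed before any treatment. A comparison of arms on the Visit 9/ET score alone carries that spread as noise, and a pre-dose test on the same person can remove part of it. The plan collects that test and defines it as baseline, but schedules no summary that uses it within person.

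At stake is how sharply the trial can describe a cognitive difference, or bound its absence, at each of four doses. The arms are small, and the SAP says that the sample size of "approximately 50 randomized participants in each of the 5 treatment groups is not based on statistical power consideration". Precision available from data already in hand is therefore worth having. The omission is not explained, and SDC is the only quantitative safety measure so treated.

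**Working it through.** The plan states no SDC effect, SD or power, so there is no figure to reproduce. The calculation below shows precision only.

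**Inputs from the documents**
- About 50 participants per arm, five arms, equal allocation (SAP sections 4 and 14).
- One SDC test before and one after dosing (schedules of activities).
- 95% two-sided intervals. The plan states these for efficacy; they are borrowed here as a yardstick.

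**Assumptions, because the documents are silent**
- r, the correlation between the Visit 1 and Visit 9/ET scores, is varied from 0.3 to 0.8.
- The SD is the same at both visits and is set to 1, so results are in units of the raw SDC SD.
- No dropout.

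**Formulas**
- SD of the quantity compared: raw score, 1; change from baseline, √(2(1 − r)); baseline-adjusted score (ANCOVA), √(1 − r²).
- 95% CI half-width for dose minus placebo = 1.96 × SD × √(2/50) = 0.392 × SD.

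**Example at r = 0.7**
- Raw: 0.392 × 1 = 0.392.
- Change: 0.392 × √0.60 = 0.392 × 0.775 = 0.304.
- Baseline-adjusted: 0.392 × √0.51 = 0.392 × 0.714 = 0.280.

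**Half-widths in SD units**

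| r | Raw Visit 9/ET | Change from baseline | Baseline-adjusted |
|---|---|---|---|
| 0.3 | 0.392 | 0.464 | 0.374 |
| 0.5 | 0.392 | 0.392 | 0.339 |
| 0.7 | 0.392 | 0.304 | 0.280 |
| 0.8 | 0.392 | 0.248 | 0.235 |

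Change beats the raw score only where 2(1 − r) < 1, that is, r > 0.5. At r = 0.5 the two are equal, and at r = 0.3 the change interval is wider (0.464 against 0.392). Baseline adjustment has 1 − r² ≤ 1 at every r, so it does not lose apart from about one degree of freedom.

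**The case against.** Several points on the other side have force.

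- **The raw comparison is not invalid.** A reader might infer that between-person spread hides any cognitive difference, or that the Visit 9/ET comparison merely reflects who landed in which arm. The documents do not support that. Randomization keeps the raw difference unbiased apart from dropout. For illustration, 50 per arm gives 70.5% power for a 0.5 SD difference on the raw score at a two-sided 5% level. Descriptive statistics by arm are planned at both visits, so a reader can see baseline imbalance and subtract the means. What is missing is the within-person change and its SD, on the same participants at both visits.
- **The gain depends on an unknown correlation.** This stands, and it is why the range must include low values. Protocol 7.7.1 also lets washout of prohibited medication start after screening, so some Visit 1 tests may precede washout, which could lower r and complicate the reading of change.
- **The comparator scales get no model or interval.** True. SAP section 11 plans only simple summaries: "Continuous variables will be summarized by number of participants and mean, SD, median, minimum, and maximum values". Consistency alone supports a change-from-baseline summary. The adjusted difference rests on precision instead.
- **Table specifications sit in a separate document.** SAP section 4 says so, and change might be tabulated there. That cannot be assumed, since the SAP spells out change for the other measures.
- **The documents do not conflict.** Correct. SAP and protocol agree on SDC, so this is an omission shared by both, not a discrepancy.

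**Conclusion.** The point holds as a minor gap in descriptive safety reporting. A baseline SDC test is collected and defined, yet neither document plans a within-person summary of it, while both do so for every other quantitative safety measure. The cost is precision, not validity. If r is 0.7 to 0.8, the raw interval of ±0.392 SD could shrink to ±0.280 to ±0.235 SD with baseline adjustment. If r is 0.3 the gain is slight (±0.374 SD). These figures rest on assumed correlations, equal SDs at both visits, about 50 per arm and no dropout.

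A reader might also infer that the repair would reveal acute cognitive effects. It would not. The only planned post-dose test is on Day 22, 7 days after the Day 15 dose, and protocol 9.3 describes a short half-life. That timing is a separate matter.

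**What to change.** In SAP 11.5.3 and protocol 10.4.2.5:

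1. Add change from baseline for each SDC parameter (n, mean, SD, median, minimum, maximum) by treatment group, in participants with both tests.
2. For correct responses at Visit 9/ET, add each dose-minus-placebo difference adjusted for baseline SDC, with a 95% CI, labelled descriptive and without a formal test.

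The first item matches what is planned for BPRS+ and CADSS. The second secures the precision even if r turns out to be low. The cost is one extra table and about one degree of freedom, with no new data. Change scores alone may be less precise than raw scores if r is below 0.5, so they should not be the only addition.

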### **11.5.4 Columbia-Suicide Severity Rating Scale**

For C-SSRS, the number and percentage of participants with suicidal ideation or suicidal behavior as recorded on the C-SSRS will be summarized by treatment group for the Safety Population. The distribution of responses for most severe suicidal ideation and most severe suicidal behavior during the participant's lifetime, during the double-blind treatment period, and during the safety follow-up period will also be presented by treatment group. Supportive listings will be provided and will include the PID number, study center number, treatment group, lifetime history, and postbaseline values. Intensity of suicidal ideation and suicidal behavior type will also be included in these listings. A listing of all AEs occurring in participants who have suicidal ideation or suicidal behavior will also be provided.

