#### 9.4.5. Columbia-Suicide Severity Rating Scale

The C-SSRS is an instrument that reports the severity of both suicidal ideation and behavior ([Appendix 12](#) and [Appendix 13](#)). Suicidal ideation is classified on a 5-item scale: 1 (wish to be dead), 2 (nonspecific active suicidal thoughts), 3 (active suicidal ideation with any methods [not plan] without intent to act), 4 (active suicidal ideation with some intent to act, without specific plan), and 5 (active suicidal ideation with specific plan and intent). The C-SSRS also captures information about the intensity of ideation, specifically the frequency, duration, controllability, deterrents, and reasons for the most severe types of ideation. Suicidal behavior is classified on a 5-item scale: 0 (no suicidal behavior), 1 (preparatory acts or behavior), 2 (aborted attempt),

3 (interrupted attempt), and 4 (actual attempt). More than 1 classification can be selected provided they represent separate episodes. For actual attempts only, the actual or potential lethality is classified for the initial, most lethal, and most recent attempts.

The C-SSRS will be completed at all study visits. At Visit 1 (Screening), the C-SSRS will be completed for the participant's lifetime history of suicidal ideation and behavior. At all other visits, the C-SSRS will be completed for ideation and behavior since the previous visit. The C-SSRS will be evaluated and signed at each visit by a qualified staff member (ie, the investigator or designee who has extensive professional training and experience in assessing mental illness), before the participant leaves the study center.

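### The planned C-SSRS summaries do not use the pre-dose record, so ideation that continues after dosing is not separated from ideation that is new or worse

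*SAP*

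**What the plan says.** SAP 11.5.4 plans two C-SSRS summaries by arm. In the first, "the number and percentage of participants with suicidal ideation or suicidal behavior as recorded on the C-SSRS will be summarized by treatment group"; that sentence names no period. The second is the distribution of the most severe ideation and behaviour "during the participant's lifetime, during the double-blind treatment period, and during the safety follow-up period will also be presented by treatment group". The listings "will include the PID number, study center number, treatment group, lifetime history, and postbaseline values". Protocol 10.4.2.5 plans the same: "The number and percentage of participants with suicidal ideation or suicidal behavior as recorded on the C-SSRS will be summarized by treatment", and "Supportive listings will be provided and will include the participant number, lifetime history, and postbaseline values".

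On collection, protocol 9.4.5 states: "At Visit 1 (Screening), the C-SSRS will be completed for the participant's lifetime history of suicidal ideation and behavior". It continues: "At all other visits, the C-SSRS will be completed for ideation and behavior since the previous visit". The schedule of activities has a C-SSRS at Visit 2 (Baseline), so a recent pre-dose value covering the lead-in will exist.

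SAP 11 sets a general rule for every safety parameter except adverse events: "the last nonmissing safety assessment before the first dose of double-blind study treatment will be used as the baseline for all analyses of that safety" (the last word of the sentence is cut here). C-SSRS is among the parameters it lists.

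**The concern.** None of the C-SSRS outputs described has a baseline column, a shift table, or a count of participants whose ideation began or worsened after dosing. Someone with the same ideation before and after dosing counts the same as someone in whom it appeared for the first time. Lifetime history cannot fill the gap, because it does not show the participant's state just before dosing.

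Suicidality is a named safety measure in protocol section 4. With about 50 participants per arm, a reader of the planned tables could not tell whether an excess on one dose arose after dosing or was already present at randomisation. Nor could they tell whether similar rates concealed a real emergent excess.

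**Working it through.** The documents give no precision or power figure for C-SSRS, and the sample size is expressly not power-based. There is no stated figure to reproduce.

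**1. Does the plan use a pre-dose reference elsewhere?** Yes.
- Adverse events count as treatment-emergent only if they began or worsened on or after the first double-blind dose (SAP 11.1).
- Laboratory and ECG PCS rates are restricted to participants with a non-PCS baseline (SAP 11.2, 11.4).
- BPRS+ and CADSS are summarised as change from baseline (SAP 11.5.1, 11.5.2).
- C-SSRS has no equivalent.

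**2. Can participants have ideation before dosing?** Yes. Protocol 6.2 excludes an attempt within the past year, investigator-judged significant risk, MADRS Item 10 of 5 or more, and imminent risk of injury. An Item 10 score of 4 can enter, and its anchor in Appendix 8 describes frequent suicidal thoughts without plan or intention. Criterion 4 in protocol 6.1 requires a rater-administered MADRS of at least 26.

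**3. How large is chance imbalance before dosing?** Let p be the pre-dose prevalence of ideation (assumed). With 50 per arm, the SD of the difference between two arms is sqrt(2p(1 − p)/50). The probabilities come from binomial simulation with five arms of 50 and 1,000,000 replicates.

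| p (assumed) | SD, points | One given dose arm differs from placebo by ≥10 points | At least one of four does |
|---|---|---|---|
| 10% | 6.0 | 13% | 36% |
| 20% | 8.0 | 26% | 62% |
| 30% | 9.2 | 33% | 72% |
| 40% | 9.8 | 36% | 77% |
| 50% | 10.0 | 37% | 78% |

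**4. How much of that reaches the on-treatment comparison?** Let B be an arm's pre-dose proportion, s the share in whom ideation continues or recurs after dosing, and e the emergent rate among the rest. The expected on-treatment rate is sB + e(1 − B) = e + (s − e)B. With equal e, a pre-dose difference is therefore multiplied by (s − e).

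- *Mimic.* Take s = 0.7, e = 0.05 in both arms, and B = 20% on placebo and 30% on drug. Placebo: 0.7 × 0.20 + 0.05 × 0.80 = 18.0%. Drug: 0.7 × 0.30 + 0.05 × 0.70 = 24.5%. The spurious excess is 6.5 points. With s = 0.5 it is 4.5, and with s = 0.9 it is 8.5.
- *Mask.* Take s = 0.7, B = 36% on placebo and 24% on drug, and e = 5% and 15%. Placebo: 0.7 × 0.36 + 0.05 × 0.64 = 28.4%. Drug: 0.7 × 0.24 + 0.15 × 0.76 = 28.2%. A 10-point emergent excess disappears.
- *Dilution without imbalance.* With B = 30% in both arms and e = 5% and 15%, the any-ideation difference is (1 − 0.30) × 10 = 7.0 points.

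**5. How often would this mislead?** One dose arm was simulated against placebo, with 500,000 replicates per scenario, pre-dose ideation 20–40% and persistence 50–90% (all assumed).

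| Truth | Misleading result | Any-ideation table | New-onset table |
|---|---|---|---|
| Emergent 15% drug, 5% placebo | No excess on drug | 18–31% of trials | 6–10% |
| Emergent 5% in both | Excess ≥10 points on drug | 10–18% of trials | 2–4% |

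The new-onset column covers participants without pre-dose ideation. Worsening among those who already had ideation was not simulated.

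**The case against.** Several counter-arguments have force.

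- **The comparison is randomised.** Every summary is by arm with placebo alongside. A reader might infer that the arms are compared with a systematic bias, or with lifetime history alone. Neither follows: lifetime is only the sole pre-dose *period* tabulated, and the problem is chance imbalance. This stands.
- **Recall limits what is counted.** A reader might infer that any past ideation is reported as on-treatment. Post-dose forms ask about the interval since the previous visit, so after Visit 2a, whose interval begins at Visit 2, ideation that ended before dosing is not counted. This stands.
- **Visit 2 is already baseline.** The schedule places Visit 2 under the double-blind heading, so a reader might infer that lead-in ideation will be counted as on-treatment. SAP 11, SAP 16.2 and the Visit 2 row of Table 16-1 point the other way. What remains is that Table 16-1 works by day and the 4-hour post-dose C-SSRS (Visit 2a) falls on the same day. One clarifying sentence is enough.
- **There is an adverse-event route.** An attempt, judged significant risk or Item 10 of 5 or more leads to withdrawal as a suicide-related AE (protocol 8.1), and the treatment-emergent rule then applies. This covers serious worsening. Milder worsening is captured only if it is recorded as an AE.
- **Table shells are in a separate document** (SAP 4). The claim is therefore limited to the outputs that the SAP and protocol describe.
- **The added counts have their own weakness.** The Visit 2 record covers at most about 7 days, while the post-dose value is the worst of eight assessments (Visits 2a to 9) over three weeks. If ideation occurred independently in 20% of weeks (assumed), 1 − 0.8³ = 49% of those negative at Visit 2 would look emergent with no change in their condition. Sampling noise also remains: at 15% against 5% with 50 per arm, 1.96 × sqrt(0.15 × 0.85/50 + 0.05 × 0.95/50) is about 12 points. Both stand, and they limit how the new counts should be read.

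**Conclusion.** The point holds in a limited form. The outputs described leave the pre-dose C-SSRS record unused, against the SAP's own baseline rule and its practice for other safety data. As a result, they cannot separate continuing ideation from new or worsened ideation.

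The omission is read directly from the text. Its size depends on prevalence, persistence and emergent rates that the documents do not give. Under the assumptions shown, a 10-point chance imbalance before dosing moves the on-treatment difference by 4.5 to 8.5 points. A reader might take the 95% chance range for pre-dose prevalence as the error in the on-treatment comparison. At 20–50% prevalence that range is 1.96 × 8.0 to 1.96 × 10.0, about ±16 to ±20 points. It describes imbalance before dosing, which is multiplied by (s − e) before it reaches the on-treatment rate. The documents also give no basis for ranking it against a drug effect.

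This is a worthwhile, cheap improvement to a descriptive safety output in a Phase 2a trial. It does not make the planned tables invalid.

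**What to change.** In SAP 11.5.4, keep the planned tables and add:

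1. A statement that the Visit 2 pre-dose record is the C-SSRS baseline and is not counted in the double-blind period, and that Visit 2a is post-dose. Name the period for the first n (%) summary.
2. A shift table by arm of pre-dose category against worst post-dose category in the double-blind period.
3. n (%) by arm with new-onset or worsened ideation, and with new behaviour, relative to that baseline.
4. The Visit 2 value in the listings.
5. A statement on whether recent-ideation recall from the Visit 1 form is added to baseline. The form in Appendix 12 has a recent-months column, while protocol 9.4.5 mentions only lifetime recall at Visit 1.
6. A footnote that the pre-dose window is at most about 7 days against three weeks post-dose, so emergent counts are raised in every arm and should be read only against placebo.

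No new data are needed. The cost is a few definitions, one shift table and one summary, plus the interpretive limit in the footnote. Protocol 10.4.2.5 is a summary and can refer to the SAP.
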